## LIST OF ABBREVIATIONS AND DEFINITIONS OF TERMS

Abbreviation	Definition
ABPM	Ambulatory blood pressure monitoring
ACE	Angiotensin converting enzyme
ADA	Anti-drug antibody
AE	Adverse event
AGT	Angiotensinogen
ALT	Alanine aminotransferase
AngI/II	Angiotensin I/II
ARB	Angiotensin II-receptor blocker
AST	Aspartate aminotransferase
CCB	Calcium channel blocker
CPC	Clinical product complaint
DB	Double-blind
DBP	Diastolic blood pressure
DMC	Data Monitoring Committee
ECG	Electrocardiogram
eCRF	Electronic case report form
eGFR	Estimated glomerular filtration rate
EOT	End of treatment
ET	Early termination
FAS	Full analysis set
GalNAc	N -acetylgalactosamine
GCP	Good Clinical Practice
HbA1c	Hemoglobin A1c
HBPM	Home blood pressure monitoring
HCV	Hepatitis C virus
HDL-C	High-density lipoprotein
HOMA	Homeostatic model assessment
ICF	Informed consent form
ICH	International Council for Harmonisation of Technical Requirements for Pharmaceuticals for Human Use
IEC	Independent Ethics Committee

IND	Investigational New Drug
INR	International normalized ratio
IRB	Institutional Review Board
IRT	Interactive Response Technology
ISR	Injection site reactions
LFT	Liver function test
MAO	Monoamine oxidase
MedDRA	Medical Dictionary for Regulatory Activities
MMRM	Mixed model with repeated measurements
mRNA	Messenger ribonucleic acid
NSAID	Nonsteroidal anti-inflammatory drug
OLE	Open-label extension
PD	Pharmacodynamics
PK	Pharmacokinetic
PT	Preferred term
RAAS	Renin-angiotensin-aldosterone system
RNAi	RNA interference
SAE	Serious adverse event
SAP	Statistical analysis plan
SBP	Systolic blood pressure
SC	Subcutaneous
siRNA	Small interfering RNA
SGLT2	Sodium-glucose co-transporter 2
THC	Delta-9-tetrahydrocannabinol
ULN	Upper limit of normal

## 1. INTRODUCTION

Alnylam Pharmaceuticals, Inc. (the Sponsor) is developing zilebesiran (ALN-AGT01), a subcutaneously (SC) administered investigational agent comprised of a synthetic small interfering RNA (siRNA) covalently linked to a triantennary *N*-acetylgalactosamine (GalNAc) ligand, which is designed to suppress liver production of angiotensinogen (AGT) and thereby reduce blood pressure in individuals with hypertension.

### 1.1. Study Rationale

Study ALN-AGT01-003 (KARDIA-2) is a randomized, double-blind, placebo-controlled, multicenter study designed to evaluate the efficacy, safety, and pharmacodynamics (PD) of zilebesiran administered SC as an add-on therapy in patients with hypertension despite treatment with a standard of care antihypertensive medication. Patients will be randomized to run-in on 1 of 3 protocol-specified antihypertensive medications open-label for at least 4 weeks (olmesartan, amlodipine, or indapamide). At the end of the Run-in period, patients with uncontrolled blood pressure will be randomized 1:1 to receive zilebesiran or placebo as add-on therapy to the protocol-specified background antihypertensive medication for 6 months during the double-blind (DB) period. After completion of the 6-month DB period, patients may be eligible to participate in a separate zilebesiran open-label extension (OLE) study. If an individual patient reaches Month 6 prior to availability of the OLE study, they may discontinue their protocol-specified background antihypertensive medication and receive open-label zilebesiran (600 mg once every 6 months) for up to 12 additional months until the OLE study is open and then transition.

The primary objective of the study is to evaluate the efficacy of zilebesiran as an add-on therapy for the treatment of hypertension by evaluating the change in 24-hour mean systolic blood pressure (SBP), assessed by ambulatory blood pressure monitoring (ABPM), from baseline to Month 3, relative to placebo. Secondary and exploratory objectives of the study include evaluating the add-on efficacy of zilebesiran on other measures of blood pressure response (including longer treatment durations, eg, 6 months) and evaluating the PD effect of zilebesiran, including reduction in circulating AGT concentration.

The full rationale for the study and design is presented in Section 3.2.

### 1.2. Background

Hypertension affects 30% to 45% of adults and is the strongest modifiable risk factor for cardiovascular disease, primarily strokes and myocardial infarction.[Olsen 2016; Williams 2018] The worldwide disease burden is profound, with a global prevalence of over 1 billion,[Kearney 2005; NCD Risk Factor Collaboration 2017] and approximately 9 million deaths attributed to hypertension annually.[Angell 2015]

Currently available pharmacologic therapies achieve target blood pressure in only a minority of patients, due in large part to physician inertia and patient nonadherence to daily oral medication.[Whelton 2018; Williams 2018] Low adherence to oral antihypertensives is associated with poor cardiovascular outcomes and is prevalent at all stages of disease.[Corrao 2011; Peacock and Krousel-Wood 2017; Schulz 2016; van der Laan 2017] Thus, despite the availability of multiple efficacious agents, current rates of control are low, and the global burden

of death and disability-adjusted life-years attributed to elevated blood pressure remains high.[Forouzanfar 2017; Muntner 2020] Development of new approaches to treat hypertension and to overcome the limitations of current therapies is a key unmet need.[Dzau and Balatbat 2019; McClellan 2019; Services 2020]

The Sponsor is developing zilebesiran, a novel synthetic RNA interference (RNAi) therapeutic, for SC administration for the treatment of hypertension. RNAi is a naturally occurring cellular mechanism for regulation of gene expression, mediated through the binding of siRNA to its complementary messenger RNA (mRNA) sequence, leading to mRNA cleavage and subsequent suppression of the synthesis and levels of the target protein. Zilebesiran contains an siRNA targeting *AGT* mRNA, conjugated to a GalNAc-containing ligand to facilitate delivery to the liver. Based on the mechanism of RNAi, zilebesiran is specifically designed to reduce the hepatic synthesis of AGT protein, the first substrate in the renin-angiotensin-aldosterone system (RAAS) and the sole precursor of vasoactive angiotensin peptides.[Khanna 2017; Romero 2015] Because hepatocytes are the predominant source of circulating AGT, zilebesiran has been developed to reduce blood pressure by decreasing circulating AGT levels and the downstream effects of angiotensin II (AngII).

Zilebesiran is being studied in the ongoing Phase 1 Study ALN-AGT01-001 (hereafter referred to as Study 001) in patients with hypertension as single ascending doses of 10 to 800 mg (Part A), as a single dose of 800 mg under low-salt or high-salt conditions (Part B), as 2 doses of 800 mg administered every 3 months in obese patients (Part D), and as a single dose of 800 mg co-administered for 2 weeks with 300 mg irbesartan (Part E). Preliminary data are available from Parts A, B, and E. Dose-dependent and durable reductions in circulating AGT were observed after single SC doses of zilebesiran, accompanied by clinically significant reductions in SBP and diastolic blood pressure (DBP). Sustained reductions in serum AGT were observed for up to 6 months following a single dose of zilebesiran.

Most adverse events (AEs) have been mild or moderate in severity, and there have been no severe or serious adverse events (SAEs) related to study drug. There have been no clinically significant elevations in serum creatinine or serum potassium. No patient has required intervention for low blood pressure. No clinically significant alanine aminotransferase (ALT) elevations have been observed in patients who received zilebesiran doses as high as 800 mg. Injection site reactions (ISRs) were reported in a minority of patients and were all mild and transient events that resolved without intervention.

Because most patients with hypertension eventually progress to require treatment with more than 1 antihypertensive class,[Williams 2018] it is anticipated that zilebesiran may be used together with other standard of care antihypertensive medication. This Phase 2 study will further quantify the antihypertensive effects of zilebesiran as add-on therapy in patients with hypertension not adequately controlled by a standard of care antihypertensive medication. The consistent and durable PD effect of zilebesiran is expected to achieve the unique benefit of continuous 24-hour blood pressure lowering with infrequent SC dosing.

A detailed description of the chemistry, pharmacology, efficacy, and safety of zilebesiran is provided in the Investigator's Brochure.

### 1.3. Benefit-Risk Assessment

Clinical data available from Study 001 indicate that zilebesiran may offer the benefit of sustained blood pressure reduction to patients with hypertension with infrequent administration (ie, once every 3 months or once every 6 months). The mean SBP reduction observed after single zilebesiran doses of 100 mg or higher exceeds 10 mmHg, which is comparable to the effect of conventional antihypertensives.[Abraham 2015; Materson 1993] The blood pressure of patients will be closely monitored, and after Month 3, escape antihypertensive medications will be added as needed to control blood pressure.

Given the mechanism of action and mode of administration of zilebesiran, potential theoretical risks include liver transaminase elevations and ISRs. Like any antihypertensive therapy, there is also a theoretical risk of hypotension with zilebesiran. Based upon the disease population, there is also a risk of blood pressure elevation. Because eligible patients have mild to moderate primary hypertension, the likelihood of disease progression during the course of the study is low. This study has exclusion criteria intended to minimize these risks, as well as frequent monitoring for laboratory and blood pressure abnormalities. Furthermore, the duration of the placebo period is limited, and escape antihypertensive medications are permitted to manage uncontrolled blood pressure following 3 months of add-on treatment with zilebesiran. Detailed guidance is provided to Investigators for potential liver transaminase elevations (Section 5.2.4), hypotension (Section 5.8.1), hypertension (Section 5.8.2), renal dysfunction (Section 5.8.3), and hyperkalemia (Section 5.8.4). An independent Data Monitoring Committee (DMC) will monitor and ensure the safety of study participants (see Section 3.6).

Based on available data from Study 001, zilebesiran has an acceptable safety profile in patients with hypertension as a monotherapy or with the addition of conventional antihypertensives in patients who were inadequately controlled on zilebesiran alone. This experience supports that the theoretical risks of treatment are low and can be managed through the proposed monitoring and safety mitigations. In addition to study drug, each patient will receive a protocol-specified background antihypertensive medication (olmesartan, amlodipine, or indapamide). These agents are approved standard medications that will be dosed in accordance with local labeling.

While zilebesiran is designed to inhibit the RAAS, its site of action (AGT) in the RAAS is unique, and its tissue specificity for the liver is hypothesized to improve its renal safety profile relative to conventional RAAS blockade,[Mullick 2017; Uijl 2019] both in the context of monotherapy and when used together with a conventional RAAS blocker such as olmesartan. In the latter setting, zilebesiran is hypothesized to add antihypertensive benefit when added to a conventional RAAS blocker without the increased incidence of RAAS inhibitor-associated renal adverse effects that have been observed in prior trials of conventional dual RAAS blockade.[Makani 2013] Patients with estimated glomerular filtration rate (eGFR)  $<45 \text{ mL/min/1.73m}^2$  or urine albumin:creatinine  $\geq 300 \text{ mg/g}$  will be exclusively assigned to the olmesartan cohort to ensure that patients with proteinuric chronic kidney disease or diabetes continue the RAAS inhibition standardly recommended for their renal indication throughout the study.

This study's monitoring plan is designed to meet the standards set by prior studies of conventional RAAS inhibitors,[McMurray 2016; Parving 2012]. The risk of renal safety events is further mitigated in this study by its eligibility criteria, which exclude patients who are at

highest risk to have events (eGFR <30 mL/min/1.73m^2, baseline serum potassium >5 mEq/L, or poorly controlled diabetes) and those who may have decreased tolerance for renal safety events (patients with clinically significant heart failure, valvular heart disease, or recent history of cardiovascular event).

Information about the known and expected benefits and risks of zilebesiran may also be found in the current edition of the Investigator's Brochure.

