- Patients may be eligible to participate in a separate zilebesiran OLE study upon completion of the Month 6 predose assessments. If an individual patient reaches Month 6 prior to availability of the separate OLE study, they may receive open-label zilebesiran beginning at the Month 6 visit and continue for up to 12 additional months until the separate OLE study is open and then transition at Month 12 or 18 (first visit after the separate OLE study is open). Patients who rollover at Month 6 should complete all assessments scheduled for the Month 6 visit except for study drug administration. Patients who rollover at Month 12 should complete the EOT visit instead of the assessments scheduled at Month 12.
- Patients who discontinue study drug at any time during the study or do not enroll in the separate OLE study will be asked to perform Safety Follow-up visits once every 6 months after the last dose of study drug until serum AGT levels return to  $\geq 50\%$  of their individual mean baseline level (if known) or 12 months, whichever comes earlier. During this Follow-up period, HBPM monitoring may continue at the discretion of the Investigator. The ADA sample should only be collected at the first Follow-up visit during the Follow-up period.
- Patients who discontinue study drug prior to the Month 6 visit will also be asked to complete the remainder of scheduled study visits and assessments (except for study drug administration) through Month 6. If a patient discontinues study drug after the Month 6 visit, EOT/ET assessments should be performed.

Footnotes:

a All assessments, except for postdose PK sample collection (Table 2), are to be performed prior to administration of protocol-specified background antihypertensive medications (including Run-In Visit 1) and study drug (as applicable).

b When applicable, pregnancy test results must be known prior to dosing with study drug at dosing visits.

c Laboratory assessments at Day 1 do not need to be repeated, per Investigator discretion, if they were collected within 7 days before Day 1 at Run-in Visit 2.

d Office blood pressure must be measured before the patient takes oral antihypertensive medications or study drug (as applicable).

e ABPM recordings associated with study drug dosing visits should be obtained within 7 days before the visit and results reviewed before dosing.

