## OLE Period

After the 6-month DB period, protocol-specified background antihypertensive medications will be discontinued, and patients may be eligible to participate in a separate zilebesiran OLE study. If an individual patient reaches Month 6 prior to availability of the separate OLE study, they may receive open-label zilebesiran at 600 mg SC once every 6 months for up to 12 additional months until the separate OLE study is open and then transition. Once the separate OLE study is open for enrollment, eligible patients may rollover into that OLE study at Month 6, 12, or 18 (first visit after the separate OLE study is open).

During the OLE period of this study, Investigators will use escape antihypertensive medications as described in [Table 4](#) to control blood pressure, guided by continued blood pressure monitoring.

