After the 6-month DB period, protocol-specified background antihypertensive medication (olmesartan, amlodipine, or indapamide) will be discontinued, and patients may be eligible to participate in a separate zilebesiran OLE study. If an individual patient reaches Month 6 prior to availability of the separate OLE study, they may receive open-label zilebesiran at 600 mg SC once every 6 months for up to 12 additional months until the separate OLE study is open and then transition. Because many patients will receive zilebesiran for the first time at Month 6, office blood pressure and serum chemistries will be monitored monthly from Month 6 to Month 9.

During the OLE period, Investigators may use escape antihypertensive medications of permitted classes as described in [Table 4](#) to control blood pressure, guided by continued blood pressure monitoring and following current care guidelines.[Whelton 2018; Williams 2018] Olmesartan, amlodipine, and indapamide will be discontinued as protocol-specified background antihypertensive medication during the OLE period; however, patients may continue to receive amlodipine or indapamide as escape antihypertensive medication at the Investigator’s discretion. The use of conventional RAAS inhibitors (ARBs, ACE inhibitors, or direct renin inhibitors) as escape antihypertensive agents for high blood pressure should be avoided throughout the study.

While the tissue specificity of zilebesiran for the liver is hypothesized to improve tolerability relative to current oral antihypertensives,[Mullick 2017; Uijl 2019] the protocol's monitoring plan is designed to meet the standards set by prior studies of conventional RAAS inhibitors[McMurray 2016; Parving 2012].

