### 5.3. Protocol-specified Background Antihypertensive Medications

All patients will be randomized to receive 1 of the 3 following standard of care oral antihypertensive medications during a Run-in period of at least 4 weeks and will continue this

protocol-specified background antihypertensive medication through Month 6. Protocol-specified background antihypertensive medications will be supplied by the Sponsor.

- Olmesartan: 40 mg orally once daily (or 20 mg orally once daily for patients with creatinine clearance  $\leq$ 60 mL/min enrolled at sites outside of the US, consistent with local labeling). At the Investigator's discretion, patients who are randomized to receive 40 mg olmesartan once daily may initiate treatment at 20 mg once daily and then uptitrate to the full dose of 40 mg once daily after 1 to 2 weeks (in this case, the patient must take the full olmesartan dose of 40 mg once daily for at least 4 weeks prior to reassessment at Run-in Visit 2).
- Amlodipine: 5 mg orally once daily
- Indapamide: 2.5 mg orally once daily

Protocol-specified antihypertensive medications may be downtitrated or temporarily discontinued per Investigator judgement for low blood pressure (see Section 5.8.1). At the Investigator's discretion, oral antihypertensive agents, including protocol-specified background antihypertensive medication, may be prophylactically held during intercurrent illness or volume depletion. Additional information on the protocol-specified background antihypertensive medications, including side effects, drug-drug interactions, and other important prescribing information can be found in the Pharmacy Manual.

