**Table 4: Recommended Interventions for Potentially Clinically Significant Blood Pressure Elevation**

Study Period	Intervention
Throughout Study	
 
• Whenever possible, management decisions should be based on blood pressure measurements confirmed by office blood pressure.
 
• Any confirmed event of severe hypertension (office SBP <math>\geq</math>180 mmHg and/or office DBP <math>\geq</math>120 mmHg) should be appropriately treated regardless of its timing relative to study drug administration.
 
• Until double-blind data are generated that demonstrate acceptable safety and added antihypertensive efficacy of zilebesiran when combined with olmesartan, the use of conventional RAAS inhibitors (ARBs, ACE inhibitors, or direct renin inhibitors) as escape antihypertensive agents for high blood pressure will be avoided throughout the study.
 
• If added, escape antihypertensives must be used per their labeled instructions and in accordance with current clinical guidelines.[Whelton 2018; Williams 2018]
 

Day 1 to Month 3	
Intervene if clinically significant blood pressure elevation:
 
 
• Because of the gradual onset of effects of zilebesiran, interventions for asymptomatic hypertension should be avoided in the first 6 weeks after the patient's first administration of study drug.
 
• After Week 6, patients who develop office SBP <math>></math>160 mmHg and increased <math>></math>10 mmHg from their baseline office SBP that persists for <math>\geq</math>24 hours on 2 consecutive measurements or that is accompanied by hypertensive symptoms should be evaluated by the clinical study site. Severely symptomatic patients should be evaluated at the clinical study site or another hospital setting within 24 hours.
 
• If persistent hypertension is confirmed (without the identification of a specific treatable cause) and the Investigator deems it to be a clinically significant change, treatment may be initiated at the medical discretion of the Investigator using a CCB and/or a thiazide/thiazide-like diuretic (whichever agent is not already the protocol-specified background antihypertensive medication) as an escape antihypertensive medication.
 

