Months 3 to 6	
Treat to target blood pressure using a CCB and/or thiazide/thiazide-like diuretic (whichever agent is not already a protocol-specified background antihypertensive medication):
 
 
• At Month 3, a CCB and/or a thiazide/thiazide-like diuretic may be added as an escape antihypertensive medication if the daytime mean SBP is <math>\geq</math>135 mmHg by ABPM. If the Investigator feels there is a compelling clinical reason to wait, the rationale for exception should be documented in the eCRF.
 
• After Month 3, other escape antihypertensive medications may also be added per Investigator judgement for persistent elevations in SBP above recommended target per treatment guidelines (eg, office SBP <math><</math>140 mmHg, HBPM SBP <math><</math>135 mmHg, or daytime mean SBP by ABPM <math><</math>135 mmHg).[Williams 2018]
 

Study Period	Intervention
Month 6 to End of Study (OLE period)	
Treat to target blood pressure using Investigator's choice of oral antihypertensive(s).
 
 
At Month 6, protocol-specified background antihypertensive medications (olmesartan, amlodipine, or indapamide) will be discontinued.
 
Patients who continue into the OLE period will initiate open-label treatment with 600 mg zilebesiran once every 6 months. As many patients will receive zilebesiran for the first time at Month 6, office blood pressure and serum chemistries will be carefully monitored monthly from Month 6 to Month 9, and Investigators will be prepared to downtitrade or interrupt escape antihypertensive medications if low blood pressure develops (see Section 5.8.1).
 
If the Month 6 ABPM is in target (daytime mean SBP <135 mmHg), escape antihypertensive medications (if taken) may be downtitrated or interrupted per Investigator judgement to determine if the patient's blood pressure remains within target on zilebesiran treatment alone.
 
During the OLE period, oral antihypertensive medications may be added per Investigator judgement for persistent elevations in blood pressure above recommended target per treatment guidelines (eg, office SBP <140 mmHg, HBPM SBP <135 mmHg, or daytime mean SBP by ABPM <135 mmHg).[Whelton 2018; Williams 2018]
 

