### 5.9.1. Prohibited Concomitant Medication

The following medications, treatments, and supplements are prohibited throughout the study treatment period (until the EOT visit):

- Conventional RAAS inhibitors (ARBs, ACE inhibitors, or direct renin inhibitors), except for olmesartan as protocol-specified background antihypertensive medication during the 6-month DB period
- Prescription NSAIDs
- Organic nitrate preparations (eg, nitroglycerin, isosorbide mononitrate, isosorbide dinitrate, pentaerythritol)
- An RNAi therapeutic (other than zilebesiran)
- Medications, herbal supplements (including Ma Huang and St. John's wort), or other substances (such as licorice) that are associated with increases in LFT abnormalities or with blood pressure abnormalities are prohibited. This includes certain stimulants (eg, amphetamine, methylphenidate dextroamphetamine, dextroamphetamine), MAO inhibitors, atypical antipsychotics (eg, clozapine, olanzapine), diet pills (eg, phenylpropanolamine, sibutramine), and nasal decongestants (eg, phenylephrine hydrochloride, pseudoephedrine, naphazoline hydrochloride).
- Medications, herbal medicines, over-the-counter medications, or supplements known to cause hyperkalemia are prohibited unless individually approved by both the Investigator and the Medical Monitor. This includes potassium-sparing diuretics, potassium supplements, cyclo-oxygenase-2 inhibitors, trimethoprim and trimethoprim-containing combination products, mineralocorticoid receptor antagonists, Noni juice, alfalfa, dandelion, horsetail, nettle, milkweed, lily of the valley, Siberian ginseng, and hawthorn berries.

All concomitant medications must be reviewed and approved by the Investigator, with particular attention to avoiding drugs that may affect blood pressure.

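### Section 1.3 promises standard RAAS inhibition for renal-indication patients for the whole study, but the operative sections end it at Month 6 for any such patient dosed in the in-study OLE

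*Protocol*

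**What the plan says.** Section 1.3 of the Protocol (Amendment 1, 22 March 2022) explains why patients with eGFR below 45 or albumin:creatinine of at least 300 mg/g go only to the olmesartan cohort: they are to "continue the RAAS inhibition standardly recommended for their renal indication throughout the study". The original protocol of 25 August 2021 carries the same sentence. Section 3.4 caps this group at 100 patients randomized to study drug.

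The operative text of the same amendment limits olmesartan to six months:

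- Section 3.1, OLE Period: "After the 6-month DB period, protocol-specified background antihypertensive medications will be discontinued".
- Section 5.3: patients stay on their "protocol-specified background antihypertensive medication through Month 6".
- Table 4, OLE row: "At Month 6, protocol-specified background antihypertensive medications (olmesartan, amlodipine, or indapamide) will be discontinued".
- Section 3.2: in the OLE, "patients may continue to receive amlodipine or indapamide as escape antihypertensive medication"; olmesartan is not given that option.
- Section 5.9.1: ARBs, ACE inhibitors and direct renin inhibitors are prohibited until the EOT visit, "except for olmesartan as protocol-specified background antihypertensive medication during the 6-month DB period".

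The OLE period belongs to this study. Under the notes to Table 1, a patient who reaches Month 6 before the separate OLE study opens may start open-label zilebesiran and "continue for up to 12 additional months until the separate OLE study is open and then transition at Month 12 or 18".

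**The concern.** Section 1.3 is the benefit-risk assessment. It offers continued standard renal therapy as the reason for the olmesartan assignment of the patients with the weakest kidneys in the trial: eGFR from 30 to below 45, or heavy albuminuria. If the operative sections withdraw that therapy halfway through a patient's participation, the document states a safety measure that the design does not deliver.

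Timing makes this more than a matter of wording. Section 1.2 reports that serum AGT stays suppressed for up to 6 months after one dose, and Section 3.3 predicts a median reduction of 94.9% at the Month 6 trough. A patient whose need for an ARB or ACE inhibitor is recognised only after the Month 6 injection can stop further dosing but cannot undo the dose already given. Adding the drug then creates the combination of zilebesiran with a conventional RAAS inhibitor that Table 4 treats with caution. The decision therefore belongs before the Month 6 dose.

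**Working it through.** No power, alpha or sample-size figure is involved. The check is a comparison of text within one version, followed by visit-day arithmetic.

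**Step 1. Does the assurance in Section 1.3 extend past Month 6?** Table 4 has a row for the whole study, separate from the rows for Months 3 to 6 and for Month 6 to the end of study, and it labels that last row as the OLE period. Section 3.8 ends a patient's study on enrolment in the separate OLE study or after Safety Follow-up. Time in the in-study OLE is therefore study time, and the assurance covers it.

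**Step 2. Do the operative sections allow it?** Sections 3.1, 3.2, 5.3 and Table 4 agree with each other that olmesartan stops at Month 6. Sections 3.2 and Table 4 bar other RAAS inhibitors only as escape agents for high blood pressure, which alone would leave room for renal use. Section 5.9.1 closes that room, because its prohibition is not limited by indication. Section 5.9, which otherwise permits any medication needed for the patient's welfare, defers to Section 5.9.1. Since the operative sections are consistent, the sentence in Section 1.3 is the one in error.

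**Step 3. Does zilebesiran itself meet the assurance?** No. Section 1.3 sets zilebesiran apart from conventional RAAS blockade, and an investigational drug is not the standardly recommended therapy.

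**Step 4. Who is affected?** Only patients in this renal group who are dosed in the in-study OLE. Those who transfer at Month 6 end this study at that point. No claim is made about patients who enter no extension.

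- Ceiling from the Section 3.4 cap: 100 patients.
- Share of the olmesartan cohort: 100 / 300 = 33.3%.
- Share of all patients randomized in the DB period: 100 / 630 = 15.9%.
- The documents do not give the share entering the in-study OLE. Assuming the cap is filled and 0%, 25%, 50% or 100% enter, the count is 0, 25, 50 or 100.

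**Step 5. For how long?** Nominal visit days from Table 1, before visit windows: Month 6 = Day 169, Month 12 = Day 337, Month 18 = Day 505.

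- Transfer at Month 12: 337 − 169 = 168 days (24 weeks).
- Transfer at Month 18: 505 − 169 = 336 days (48 weeks), the protocol maximum.
- Transfer at Month 6: 0 days.

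**The case against.** The strongest reply is that the protocol already handles a patient who needs one of these drugs. Section 4.3.1 lists required treatment with a prohibited medication among the reasons to discontinue study drug, at the investigator's discretion, and then allows treatment by local standard practice. Section 4.3 lets the investigator stop study drug at any time in the patient's interest, and the Section 5.9.1 prohibition ends at the EOT visit. Entry to the OLE is also optional. All of this stands. A reader might infer that such a patient is left with no route to standard therapy; the documents do not support that. What they lack is a prompt before the Month 6 dose. Section 4.3.1 reacts to a need once it has arisen. By contrast, Section 3.1 explicitly returns run-in failures to their prior regimen.

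A reader might also infer that the withdrawal has no rationale at all. That goes too far. Table 4 avoids conventional RAAS inhibitors as escape agents "Until double-blind data are generated that demonstrate acceptable safety and added antihypertensive efficacy of zilebesiran when combined with olmesartan". This is a partial rationale: it addresses blood-pressure escape, not a renal indication. Safety monitoring also continues in the OLE, with monthly chemistry from Month 6 to Month 9, action rules for eGFR and potassium, a data monitoring committee and renal adjudication.

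Third, Amendment 1 is apparently not the latest version. The file also holds the closing part of another version that differs in detail; for example, it allows 7 days to repeat an invalid ABPM where Amendment 1 allows 4. Its Section 7.2.1 shows that it keeps an OLE period, but its Sections 1.3, 3.1, 3.2, 5.3, 5.9.1 and Table 4 are not shown. An error in the current protocol is therefore not established.

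Finally, the Month 6 stop is stated plainly in several places, so an investigator who reads the whole protocol will probably see it. That lowers the risk of being misled but does not make the assurance true.

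**Conclusion.** The point holds for Amendment 1 and for the original protocol, within limits. The assurance in Section 1.3 is false for any patient with eGFR below 45 or albumin:creatinine of at least 300 mg/g who is dosed in the in-study OLE, for a nominal 168 to 336 days. The number of such patients is unknown: 100 is a ceiling set by the cap, and the true figure could be near zero if the separate OLE study opened in time. The ceiling should not be read as an estimate.

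Nor should the point be read as touching the trial's results. Olmesartan continues through Month 6, so the Month 3 primary analysis, the key secondary endpoints through Month 6, the sample size and the renal protection in the DB period are unaffected. This is a misstated safety measure that should be corrected. Confidence is medium, because the relevant sections of the apparently later version cannot be checked.

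**What to change.** First confirm whether the later protocol version already resolves this. If it does not:

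1. In Section 1.3, limit the assurance to the 6-month DB period.
2. In Section 3.1 or Table 4, state that a patient whose investigator judges an ARB or ACE inhibitor necessary for a renal indication should not be dosed in the in-study OLE and should return to standard care at Month 6. This places the decision before the long-acting dose.

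The cost is two sentences, with no new visits, drug supply or analysis. The downside is slightly fewer patients in the OLE.

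Continuing olmesartan alongside zilebesiran in the OLE is a different and more expensive choice. It would precede the double-blind safety data that Table 4 waits for. After Month 9 (Day 253) the only scheduled visits are Month 12 and Month 18, with gaps of 337 − 253 = 84 days and 505 − 337 = 168 days, so it would probably need added potassium and creatinine checks as well as drug supply. It should be considered only once those data exist and with the agreement of the data monitoring committee.
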